- a. Study design, including the sequence and timing of study procedures (distinguish research procedures from those that are part of routine care).

The proposed study is a 12-week, parallel design, placebo-controlled pilot trial. For the purposes of this study, we will recruit 30 participants with ASD aged 3-8 who are currently enrolled in an EIBI program. ASD is defined in this study by the DSM-V criteria plus Autism Diagnostic Observation Schedule (ADOS) criteria for Autism. Participants will be screened for this formation as well as inclusion/exclusion criteria to determine their eligibility to participate in this study over the phone prior to obtaining written consent. A waiver of documentation of consent is requested for these screening purposes only. Written consent will be obtained prior to any other study-related procedures. The ADOS may be administered during the initial study visit if a prospective participant does not have ADOS scores from a previous assessment. Additionally, an intellectual assessment (IQ test), the Differential Ability Scales (DAS), may be administered at this time if previous scores do not exist.

Prior to participation in the study, informed consent will be obtained from both parents/legal guardians of the participant, and assent will be obtained from the participant. In addition, the parents and participants will be informed that they can terminate the procedure and exit the study at any time.

We will recruit participants during their participation in the EIBI program at the Thompson Center or other institutions in Missouri. The EIBI team provides one-on-one instruction for individuals with ASD, as they work toward treatment goals of learning new skills and minimizing challenging behavior. EIBI staff will be also be blinded to drug conditions. Given the highly individualized nature of EIBI, each participant's therapy will differ in frequency of sessions per week and length, as well as defined behavioral targets and the methods used to reach them. This variability will be accounted for via a stratified randomization approach (see below) as well as statistically during analyses after study completion.

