Upon study enrollment, participants will be randomized to receive either placebo or propranolol for a period of 12 weeks during the study. Drug randomization will be counterbalanced to ensure that half of the participants will receive placebo and the other half will receive propranolol. Randomization will also be double-blinded so that neither participants nor the researchers performing analysis will be aware of the identity of the drug being administered. As participants will be receiving varying levels of intensity of EIBI (number of hours per week), randomization will also be stratified according to different levels of intensity to ensure approximately equal distribution of EIBI intensity between the two drug groups.

The following are brief descriptions of the drugs to be administered:

Propranolol [pro-pran'-o-lol] blocks the brain's and body's use of norepinephrine both centrally and peripherally and also is commonly used to decrease high blood pressure.

Placebo [pla-see'-bo] is a physiologically inactive suspension that looks like other drugs.

Drug administration: Propranolol will be administered in the form of a liquid dose via oral syringe by the participants' parent/caregiver an hour before each EIBI session. Drug administration will begin after the first (baseline) study visit. To minimize risk, the bodyweight adjusted minimum dose of propranolol used safely for test anxiety in healthy adults (10mg) will be used (see table below):

Bodyweight (kg)	Dose (mg)
> 30	4
22.5 - 30	3
15 - 22.5	2
< 15	N/A

This more cautious dosing strategy will be utilized for safety purposes, as children may be less able to report potential side effects. Participants weighing less than 15kg will be excluded for safety reasons.

Heart rate and blood pressure monitoring: Participants with a heart rate of less than 60 or a systolic blood pressure of less than 75 at the outset of the study will be excluded. Heart rate and blood pressure will also be measured via wrist cuff at each study visit. If on any measurement the heart rate or systolic blood pressure is abnormal, the PI will be immediately notified. At this point, the PI may withdraw the participant from the study for safety reasons.

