During the study, participants will undergo ANS activity and behavioral assessments (discussed below) at three separate study visits at the following time points: (1) prior to drug administration, for establishment of a baseline (week 0); (2) at approximately week 6; and (3) at the end of week 12. Each study visit is expected to last approximately an hour and half.

ANS Measurements: At each study visit, ANS measurements will be performed to assess autonomic activity. Heart rate variability (HRV), measured via electrocardiogram, will be used to assess sympathetic and parasympathetic nervous system activity. Electrodes will be placed on the chest region in the typical manner, and signal from the electrodes will be amplified by an ECG 100C module connected to a BIOPAC MP150 data acquisition system. Measurements will be recorded for a period of 8 minutes, allowing for 3 minutes of acclimation to the equipment.

We will also evaluate ANS activity via the pupillary light reflex (PLR), a simple functional neurological test measuring pupil constriction and recovery in response to stimulation via a short light flash. During the test, the participant will sit comfortably in a

chair or will be seated on a parent's lap about 1 m from the PLR system. A red-filtered movie will be shown on a projector screen behind the PLR system to attract the participant's attention. During the test, participants' PLR will be assessed in both light- and dark-adapted conditions. A total of 10 trials, each lasting 2.5 sec followed by a 25-30 sec interval, will be performed for each stimulation condition.

Behavioral Assessments: Behavioral tasks and questionnaires will also be performed at each study session. The following assessments will be completed by the participant with ASD:

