(2) Interval Medical History Questionnaire: Participants' parents/caregivers will complete a questionnaire about any side effects their child has experienced since the previous study visit, any new medical or psychiatric diagnoses, and any concomitant medications they are taking or have added since the last study visit, and whether they have visited a doctor's office or hospital since their last study visit. This questionnaire is for the purpose of maintaining the safety of participants, as the study staff and PI

will need to ensure that each participant is not experiencing any adverse events throughout the study.

(3) Demographic questionnaire: A questionnaire ascertaining a participant's personal and family demographic information, such as race/ethnicity, handedness, and socioeconomic status, will be completed by the parent/caregiver at the initial study visit only.

(4) Social Responsiveness Scale, second edition (SRS): This 65-item, parent-report measure asks questions about a participants' social awareness, social information processing, capacity for reciprocal social responses, social anxiety or avoidance, and characteristic autistic preoccupations or traits. Depending on the child's age, the preschool or school-age version of the SRS will be administered.

(5) Clinical Global Impression of Change (CGIC) and Clinical Global Impression of Severity (CGIS) scales: To assess overall changes in the participant's ASD-related clinical symptoms, the CGIC and CGIS will be administered. The CGIC consists of a 7-point subjective scale assessing change from baseline. On this scale, scores of 1, 2, and 3 represent marked, moderate, and mild improvement, respectively. A score of 4 represents no change. Scores of 5, 6, and 7 represent mild, moderate, and marked worsening, respectively. CGIC scores from both the parent/caregiver and a blinded clinician will be utilized. The CGIS is a similar 7-point subjective scale for severity.

(6) Autism Impact Measure (AIM): The AIM will be administered to assess the frequency and impact of a participant's ASD-related symptoms. A parent/caregiver is asked a series of 41 questions regarding the frequency and the impact, or interference resulting from, a series of autism-associated behaviors. Overall impact and frequency scores, as well as subscale scores, will be obtained from this measure.

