(7) Vineland Adaptive Behavior Scales-II (VABS): To assess overall adaptive functioning, the VABS will be administered in the form of a structured interview with the parent/caregiver. The VABS is a well validated assessment used for the full range of our subjects' ages and yields standard scores in Communication, Daily Living Skills, Socialization, and Motor Skills. VABS scores for Communication, Daily Living Skills, and Socialization will be monitored in this study.

(8) Aberrant Behavior Checklist (ABC): To assess overall behavioral disturbances, a parent/caregiver of the participants will complete the ABC. This 58-item questionnaire is a well validated, reliable, and widely used assessment tool for interventions for a range of cognitive disorders.

(9) Preschool Anxiety Scale (PAS): To assess anxiety, the PAS will be completed by a parent/caregiver. This 34-item parent-report questionnaire, adapted from the Spence Children's Anxiety Scale (SCAS), yields a total score and five subscale scores based on DSM-IV anxiety disorder structure (separation anxiety, social phobia, obsessive-compulsive disorder, and generalized anxiety), as well as fears related to physical injury.

We will also make efforts to gain the input of participants' parents/caregivers at the outset as well as completion of the study. This will involve the completion of a survey upon study enrollment asking about potential outcomes the parent/caregiver wishes to explore (e.g., gastrointestinal symptoms) in this study. Any suggestions that are not already incorporated to the study and are deemed appropriate and necessary by the PI will

be submitted to the HS IRB as an amendment. Additionally, after completing the study, the participants' parents/caregivers will be asked to complete an exit survey, asking about their child's experience of the study and if they have any suggestions for future studies of a similar nature. This survey will be given to parents/caregivers to complete at the end of the final study visit or mailed when necessary.

We will also make efforts to inform families of the progress of this study via newsletters containing enrollment updates and new (non-study related) findings and news in autism research sent via email on a quarterly basis. Each newsletter will be submitted to the HS IRB for approval prior to being sent out.

b. Study duration and number of study visits required of research participants.

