To determine the appropriate sample size for this study, we conducted a power analysis based on effect size estimates on our previous study examining the effects of propranolol on social functioning in ASD. The power analysis indicated that a sample size of 20 would achieve a proposed power of 0.80 at the significance level of $\alpha = .05$. Behavioral assessments will be compared across study time points and between drugs (propranolol and placebo) using repeated measures multivariate analyses of variance (MANOVAs). We will use simple linear regressions to determine whether variability in baseline autonomic nervous system functioning or anxiety serve as markers to predict treatment response. Interim data analysis will only be conducted for the purposes of presenting preliminary data at academic conferences. The investigational pharmacy will assist in unblinding collected data for these preliminary analyses, keeping investigators blinded throughout the study.

- d. Early stopping rules.

As this is a pilot trial exploring the effects of propranolol on social and language abilities, there are no behavioral endpoints that we could consider treatment success or failure prior to the completion of the study, thus we would not stop the study based on early evidence of treatment efficacy or futility. If safety becomes a concern due to side effects associated with propranolol, the PI (in consultation with the HS IRB) may decide

to stop the study early. However, this is not expected to occur given the minimal side effects known to be associated with this drug at these doses.

8. Risks

- a. Medical risks, listing all procedures, their major and minor risks and expected frequency.

The medical risks participants may encounter are those associated with taking the drugs used in this study. Below are the descriptions and side effects associated with each drug:

Propranolol [pro-pran'-o-lol] is commonly used to decrease high blood pressure. This drug can cause problems for persons with depression, diabetes, thyroid disease, very slow heart rates, very low blood pressure, fluid in the lungs from heart failure, and asthma. The side effects related to this drug are given below. These symptoms are most present within 5 hours of the drug administration. None of these symptoms will be present once the single dose is washed out of the system, which can take up to 24 hours.

- Very Likely: Decreased Blood Pressure and/or Slow Heart Rate

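### Section 7c's repeated-measures MANOVAs drop children with any missing score in a model and dilute the test of the two primaries; a mixed model per outcome is the better choice

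*Combined protocol and SAP*

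**What the plan says.** Section 7c of the combined protocol and SAP gives one sentence for all behavioral comparisons: "Behavioral assessments will be compared across study time points and between drugs (propranolol and placebo) using repeated measures multivariate analyses of variance (MANOVAs". It does not say which scores share a model, who is in the analysis set or what happens to a missing score.

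The rest comes from other sections:

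- Section 4a, sample and allocation: "we will recruit 30 participants with ASD aged 3-8 who are currently enrolled in an EIBI program", and "Drug randomization will be counterbalanced to ensure that half of the participants will receive placebo and the other half will receive propranolol".
- Section 4a, timing: "behavioral assessments (discussed below) at three separate study visits", at weeks 0, 6 and 12.
- Sections 7a and 7b: GSOM and SRS are primary. PAS, PLS-4, Vineland, CGIC, CGIS, ABC and AIM are secondary.
- Section 4a, Behavioral Assessments: several instruments give more than one score. For example, "VABS scores for Communication, Daily Living Skills, and Socialization will be monitored in this study", and "CGIC scores from both the parent/caregiver and a blinded clinician will be utilized". The CGIC rates change from baseline, so it has no baseline value.
- Section 7c, sample size: "The power analysis indicated that a sample size of 20 would achieve a proposed power of 0.80 at the significance level of" 0.05. The effect size is not given.
- Section 4a also promises that differences in EIBI will be allowed for in the analysis, without saying how.

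**The concern.** A classical MANOVA needs a full set of scores from each child. Gaps are foreseeable here. Families may leave at any time, the investigator may withdraw a child, and two instruments are given directly to children aged 3 to 8 with autism. The PLS-4 is described as made for children through age 7, while age 8 is eligible. Within any one model, a child who misses one visit or refuses one task is lost for scores that were in fact measured. In a trial of 30 that costs power. If the loss is related to how the child was doing earlier, it also biases the estimate.

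The joint test has a second cost. It spreads the evidence over every score-by-time contrast in the model. It also answers whether anything moved, not whether GSOM or SRS moved, although section 7a names both as primary.

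**Working it through.** **Inputs.** From the document: 30 children, 1:1 (15 per arm), three visits, two primaries. Error df = 30 − 2 = 28. Assumed, because the document gives no figures: missingness of 3%, 5% and 10%, correlation of 0.6 between visits, and the effect size d.

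**The plan's own figure.** The sample size of 20 cannot be reproduced, because effect size, sidedness and test are not given. Solving backwards, two-sided with 80% power, 20 implies d = 1.32 if it means 10 per arm, or 0.66 if it means 20 paired observations.

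**Complete cases, two primaries.** There are 2 scores × 3 visits = 6 cells. If cells go missing independently, the expected number complete is 30(1 − m)^6. If GSOM and SRS are lost together because a visit is missed, it is 30(1 − m)^3.

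| Missing, m | 30(1 − m)^6 | 30(1 − m)^3 |
|---|---|---|
| 3% | 25.0 | 27.4 |
| 5% | 22.1 | 25.7 |
| 10% | 15.9 | 21.9 |

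**Power on complete cases.** For a single contrast, power comes from the noncentral F(1, N − 2) with noncentrality d²N/4. Power 0.80 at N = 30 needs d = 1.06, giving 1.06² × 7.5 ≈ 8.42. With the same d, power is about 0.72 at N = 25, 0.66 at 22 and 0.51 at 16.

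**Joint drug-by-time test.** With p contrasts the denominator df is 28 − p + 1. Noncentrality is held at 8.42, meaning that only one contrast moves and it is uncorrelated with the others.

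| Scores in the model | p | Test | Power |
|---|---|---|---|
| One contrast of one outcome | 1 | F(1,28) | 0.80 |
| One outcome, three visits | 2 | F(2,27) | 0.69 |
| GSOM and SRS | 4 | F(4,25) | 0.54 |
| Nine instrument totals | 17–18 | F(17,12)–F(18,11) | 0.17–0.15 |
| All 14 component scores | 26 | F(26,3) | 0.07 |

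The 14 scores are GSOM, SRS, PAS, PLS-4 (2), VABS (3), CGIS, ABC, AIM (2) and CGIC (2). Twelve have a baseline and give two contrasts each. The two CGIC scores give one each: 12 × 2 + 2 × 1 = 26. With 27 complete children the denominator df is 25 − 26 + 1 = 0, and the test cannot be computed.

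**What a mixed model recovers.** I compared the variance of the week-12 change contrast, with correlation 0.6 at all lags and the covariance treated as known. Relative to no missing data, complete-case variance is 1/(1 − m)^6 = 1.20, 1.36 and 1.88 at 3%, 5% and 10%. Summing the information over all observed visit patterns, the per-outcome likelihood model gives 1.04, 1.07 and 1.16. The reduction is about 13%, 21% and 39%. If whole visits are missed, complete-case variance is 1/(1 − m)^3 = 1.10, 1.17 and 1.37, and the reduction is about 5%, 8% and 16%. If only week 12 is missing, in 10–20% of children, it is 3–6%.

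**The case against.** The strongest reply is that much of the damage depends on a model that the plan never describes. A reader might infer that all scores enter one MANOVA and use up nearly all 28 error df. The documents do not support that. Section 7c says MANOVAs in the plural, and sections 7a and 7b separate primary from secondary outcomes. For the same reason, a missing PLS-4 removes a child from the primary test only if PLS-4 shares that model. Nor would losing one child make an all-score test impossible: because the CGIC has no baseline, 29 complete children leave 2 df and 28 leave 1. All of this stands. The grouping is unspecified, and the 26-contrast case is only conditional.

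The loss may also be milder than the independent-cell figures. GSOM and SRS are collected at the same visits, so whole-visit loss is plausible. If the planned 20 meant 10 per arm (d = 1.32), recruiting 30 leaves a margin: single-contrast power would be about 0.89 with 25 complete children and 0.84 with 22.

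The omnibus test is not always weaker. The objectives expect improvement in several domains. If two uncorrelated contrasts moved equally, noncentrality would double to 16.8 and F(4,25) would have power of about 0.86. The 0.54 therefore describes a narrow effect.

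Finally, this is a pilot, MANOVA is valid on complete data, and separate models bring multiplicity. Two independent tests at 0.05 have familywise error 1 − 0.95² ≈ 0.098. Testing one primary at 0.025, the first Holm step, lowers the 0.80 above to about 0.70. That is still above 0.54 for the same narrow effect. None of these replies supplies a rule for missing scores or shows which primary moved.

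**Conclusion.** The point holds in limited form and should be fixed, though it does not invalidate the trial. The firm parts are three: the only named method, as ordinarily fitted, discards observed data within each model; no alternative handling is given; and the joint test of the primaries cannot attribute an effect to GSOM or SRS.

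The size is conditional. In a two-primary model, about 25 to 16 of 30 children remain at 3–10% independent missingness, or about 27 to 22 if whole visits are missed. The fall in power from 0.80 to 0.54 assumes that one contrast moves, uncorrelated with the rest, and shrinks or reverses if several move.

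A reader might also infer that a mixed model would restore almost all the lost power. The calculations do not show that. The gain is clear for scattered gaps, modest for missed visits and small if most missingness is whole-child dropout.

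**What to change.** In section 7c, replace the MANOVAs with one linear mixed model for repeated measures per outcome:

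- Terms: arm, visit, arm-by-visit and EIBI-intensity stratum, with unstructured covariance and small-sample degrees of freedom. Model the CGIC at post-baseline visits only.
- Analysis set: every randomised child with any available score on that outcome.
- Reporting: the arm difference at each visit, with its interval.
- Multiplicity: a stated rule for GSOM and SRS, for example Holm, with secondary outcomes labelled exploratory.

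This should be settled before any of the unblinded conference analyses that section 7c allows.

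The cost is a short rewrite and standard software, with no new data or participants. There are three downsides: the models rely on missing at random, each primary faces a somewhat stricter threshold, and little is gained if children mostly drop out altogether. If the MANOVAs are kept, section 7c should at least say which scores enter each one and how missing scores are handled.

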In the proposed serial-dose, parallel design study, we plan to explore the effects of propranolol in combination with early intensive behavioral intervention in children with autism. Propranolol or placebo will be administered at the beginning of behavioral intervention sessions in a double-blinded, counterbalanced manner for the course of twelve weeks. Outcome measures will include assessments of social functioning, language, anxiety, adaptive behaviors, and other autism-related symptoms. This study will allow us to examine the effects of propranolol with multiple doses in a trial setting. In addition, this will be the first exploration of this drug's effects in children with autism, an important area of study given the benefits of early intervention. Previous studies involving pediatric migraine suggest that this drug can be used safely in young children. We will also determine whether measures of autonomic nervous system functioning and anxiety can predict which individuals will respond best to the drug. In this manner, we can begin to optimize and individualize combined treatment approaches for treating core symptoms of autism.

2. Objectives (include all primary and secondary objectives)

We propose to examine the effects of propranolol on social interaction in children with autism undergoing early intensive behavioral intervention (EIBI) in a 12-week, double-blinded, placebo-controlled pilot trial. We will also assess the effects of this combined therapeutic approach on language, anxiety, adaptive behaviors, and other autism-related behaviors in these individuals. Lastly, we will investigate how autonomic nervous system (ANS) activity, as measured by heart rate variability and pupillary light reflex, and baseline anxiety might predict the effects of propranolol on social functioning and our other outcome measures. We hypothesize that concomitant administration of propranolol will enhance the clinical benefit made through EIBI by improving social functioning, language, anxiety, adaptive behaviors, and other autism-related behaviors. We predict that this augmentation of EIBI's effects will only be apparent for the propranolol condition of the study. We also expect that ANS activity and anxiety levels will predict response to propranolol on our outcome measures.

3. Background (briefly describe pre-clinical and clinical data, current experience with procedures, drug or device, and any other relevant information to justify the research)

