Participation in this study will last 12 weeks and will involve 3 visits to the Thompson Center for Autism & Neurodevelopmental Disorders lasting approximately an hour and a half each. If a private room is not available at the Thompson Center when a participant's visit needs to be scheduled, the visit will take place at the Center for Translational Neuroscience (M741) in the Medical Sciences Building instead.

c. Blinding, including justification for blinding or not blinding the trial, if applicable.

This study will be double-blinded for the purposes of removing any bias that could be introduced if either the researchers or the study participants are aware of which drug they are taking at a given time. Blinding of the drugs will be conducted by the University Hospital's Investigational Pharmacy. In the case of emergency, the PI and research staff running study sessions will have access to unblinding information in the form of a sealed envelope.

d. Justification of why participants will not receive routine care or will have current therapy stopped.

Routine care for this population will not be affected by this study. Participants will be able to continue routine care, including behavioral therapy or other medications. Potential participants taking medications that are exclusionary for this study will not be enrolled.

e. Justification for inclusion of a placebo or non-treatment group.

A placebo arm of this study will allow for statistical comparisons between behavioral performance for participants who are taking placebo versus propranolol. The parallel design of the trial will involve half of the participants receiving propranolol and the other half receiving placebo. Drug randomization will be counterbalanced.

f. Definition of treatment failure or participant removal criteria.

As this is a pilot trial exploring the effects of propranolol on social and language abilities, there are no behavioral endpoints that we would consider treatment failure. However, for the safety of the participants, if at any measurement taken, a participant's heart rate or blood pressure is abnormal or if the participant is experiencing an adverse reaction to the drug the PI will be immediately notified. At that point, if the PI determines it is necessary, the participant will be instructed to discontinue taking the drug and will be removed from the study.

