d. Legal risks such as the risks that would be associated with breach of confidentiality.

The risk of loss of privacy is minimized as the data will be coded, password-protected, and stored separately from the consent and screening forms in a locked filing cabinet. However, in the unfortunate event that a loss of privacy occurs, it is

possible that information related to a participant's autism diagnosis and performance on the tests being administered will be obtained.

e. Financial risks to the participants.

There are no expected financial risks associated with this study. However, in the event of an injury associated with the study, participants may be responsible for paying for medical expenses associated with that injury. This determination would be made in consultation with the University of Missouri Risk Management Officer.

9. Benefits

a. Description of the probable benefits for the participant and for society.

It is possible that participants may experience benefit on the behavioral assessments of social functioning, language abilities, anxiety, and global and adaptive functioning in the propranolol condition. Otherwise, there are no direct benefits to the participant. If propranolol is shown to improve ASD-related symptoms, with the greatest benefits being for those with the greatest dysregulation in autonomic activity, propranolol may be used to treat others with similar conditions.

10. Payment and Remuneration

a. Detail compensation for participants including possible total compensation, proposed bonus, and any proposed reductions or penalties for not completing the protocol.

Participants will be compensated \$25.00 for each completed study visit they complete, for a total of \$75.00 if they complete all three study visits. Furthermore, participants will be compensated \$25.00 for diagnostic testing, if needed, via the Autism Diagnostic Observation Schedule (ADOS) and \$25.00 for IQ testing, if needed, via the Differential Ability Scales (DAS). If a participant lives more than 50 miles from Columbia, MO, the family will be eligible for a flat rate of \$75 per visit to offset of costs of travel to the Thompson Center. If a family is eligible for travel funds, they could be paid a maximum of \$225 for travel-related expenses. Payments will be mailed in the form of a check within approximately one month after each study visit.

11. Costs

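### The regressions planned to show who responds to propranolol contain no arm or arm-by-marker term, so they cannot separate drug response from general progress under EIBI

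*Combined protocol and SAP*

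**What the plan says.** Section 2 sets out to learn how autonomic activity and "baseline anxiety might predict the effects of propranolol on social functioning and our other outcome measures", and ends by expecting these measures to forecast the response to propranolol. The abstract (section 1) undertakes to find out whether they "can predict which individuals will respond best to the drug". Section 9a, on the condition that the drug is shown to work, looks ahead to its use in others, "with the greatest benefits being for those with the greatest dysregulation in autonomic activity".

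The only analysis for this objective is one sentence in section 7c: "We will use simple linear regressions to determine whether variability in baseline autonomic nervous system functioning or anxiety serve as markers" of treatment response. It does not define treatment response, and it does not say whether the regressions use all children or only those on propranolol. Arm appears in section 7c only in the repeated measures MANOVAs, which carry no baseline marker.

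Three other statements bear on the point:

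- Section 4e justifies the placebo arm by the need for "statistical comparisons between behavioral performance for participants who are taking placebo versus propranolol".
- Section 5 requires every child to be in an EIBI program throughout the study.
- Section 4a says that differences in EIBI will be handled by stratified randomization "as well as statistically during analyses after study completion".

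**The concern.** Predicting the effect of a drug is a treatment-by-marker question. In a parallel design no child is observed on both drug and placebo, so an individual drug response is never seen. The question can be answered only by comparing the marker's slope between the arms.

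A one-predictor regression does not do this. Pooled over both arms, its slope averages the two. In the propranolol arm alone, there is no placebo slope to set against it. Either way the slope mixes the marker's relation to progress under EIBI with any change in the drug effect.

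Two smaller matters follow. If response means a change score, baseline anxiety against change in anxiety has a negative slope from regression to the mean alone; this applies directly to that pairing only. And a model with one predictor leaves no room for the EIBI adjustment, if that adjustment was meant to cover these regressions.

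At stake is the claim itself. The abstract hopes to start tailoring combined treatment to the individual from this work. A marker of who does well under EIBI could be reported as a marker of who should be given propranolol.

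**Working it through.** **Inputs from the protocol.** 30 children, half per arm, so 15 per arm (section 4a); α = .05 (section 7c; two-sided is assumed, as sidedness is not stated); three markers (heart rate variability, pupillary light reflex, baseline Preschool Anxiety Scale, PAS); nine outcome instruments (sections 7a and 7b). The protocol gives no marker–outcome correlation and no retest correlation for the PAS, so both are assumed and shown as ranges. The sample size of 20 in section 7c concerns the drug effect on social functioning, so there is no figure for these regressions to reproduce.

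**Step 1: what each slope estimates.** Let A be arm (0 placebo, 1 propranolol) and M the marker:

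Y = a + τA + βM + γ(A × M) + e

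Here β is prognosis under EIBI and γ is the change in drug effect per unit of marker. The objective concerns γ. With 1:1 allocation:

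- regression on all 30 children targets β + γ/2;
- regression on the propranolol arm targets β + γ;
- the arm-by-marker coefficient targets γ.

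If γ = 0, the first two are still non-zero whenever β is non-zero.

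**Step 2: how often this misleads.** Simulation, 40,000 trials per setting, τ = 0 and γ = 0. Percentage of trials significant:

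| Assumed marker–outcome correlation | 0 | 0.1 | 0.2 | 0.3 | 0.4 | 0.5 |
|---|---|---|---|---|---|---|
| Simple regression, all 30 | 4.9 | 8.0 | 18.6 | 36.8 | 60.6 | 82.8 |
| Simple regression, propranolol arm (15) | 5.1 | 6.3 | 10.9 | 19.1 | 32.3 | 49.9 |

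The arm-by-marker test rejects in 4.9–5.1% throughout. The pooled figures depend somewhat on τ: at a correlation of 0.3, a drug effect equal for all children of 0.5, 1.0 or 1.3 SD lowers the pooled rate from about 37% to 35, 30 or 26%.

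**Step 3: the opposite error.** Let the slopes be −b/2 on placebo and +b/2 on propranolol, with b = r/√(1 − r²) and τ = 0.5. For r = 0.3, 0.5 and 0.6 the pooled regression is significant in only 5, 6 and 6% of trials, against 12, 30 and 45% for the interaction. Pooling can therefore also miss a true modifier.

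**Step 4: baseline PAS against change in PAS.** With equal variances and retest correlation r, the correlation of change with baseline is −√((1 − r)/2). For r = 0.6 this is −√0.2 = −0.447.

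| Assumed retest correlation | 0.6 | 0.7 | 0.8 | 0.9 |
|---|---|---|---|---|
| Correlation of change with baseline | −0.447 | −0.387 | −0.316 | −0.224 |
| % significant, n = 30 | 72.3 | 58.0 | 40.6 | 22.3 |
| % significant, n = 15 | 40.5 | 30.5 | 21.0 | 12.3 |

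Arm × baseline PAS, tested on week-12 PAS, stays at 4.8–5.1%.

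**Step 5: number of tests.** 3 markers × 9 instruments (GSOM, SRS, PAS, PLS-4, Vineland, CGIC, CGIS, ABC, AIM) = 27 pairs before subscales. 27 × 0.05 = 1.35 nominally significant results expected by chance.

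**Step 6: precision of the correct test.** Interaction model adjusted for the outcome's baseline, without an EIBI term, residual SD 1, 15 per arm:

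| Slope difference (residual SD per SD of marker) | 0.3 | 0.5 | 0.8 | 1.0 | 1.1 | 1.2 |
|---|---|---|---|---|---|---|
| Power, % | 11.2 | 22.2 | 48.0 | 65.5 | 73.4 | 80.2 |

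The median half-width of the 95% confidence interval is about 0.83.

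**The case against.** **The model is never written out.** The absence of arm terms is inferred from the word simple and from silence. That is true, but no arm term, interaction or comparison of slopes is named anywhere for the markers. If simple was meant loosely, the sentence still needs correcting.

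**Separate regressions in each arm, set side by side, also fit the text.** This reading is fair and gives smaller error rates. For a purely prognostic marker, the chance of a significant slope on propranolol but not on placebo is p(1 − p), where p is the propranolol-arm rate above. That gives about 5/6/10/15/22/25% for correlations of 0 to 0.5; for example 0.499 × 0.501 = 0.25. The problem shrinks but remains, because comparing two significance statements is not a test of the difference in slopes.

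**The side points are weak.** The EIBI adjustment may have been meant for the MANOVAs only. Regression to the mean touches one pair of 27 and requires change scores. The count of 27 is the same for interaction tests. All three are correct, and the main point does not rest on any of them.

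**This is the last objective of a pilot, and the correct test has little power.** Both are true. They argue for exploratory reporting with an interval. They do not argue for a slope that is significant more often because it answers a different question. Relabeling the regressions as prognostic would be accurate, but it would leave the objective without an analysis.

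**Conclusion.** The concern holds. As written, the plan has no analysis able to answer whether the markers predict the effect of propranolol. This follows from the structure of the model and needs no assumed number.

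Its size does depend on assumptions: the marker–outcome correlation, a common slope in both arms, no drug effect, normal data and 15 completers per arm. Even at a correlation of 0.2 the pooled regression is significant in about 19% of trials, nearly four times the nominal rate; at zero correlation there is no excess. These results are errors only if the slope is reported as predicting response to propranolol, which is how the objective is framed. The primary comparison of propranolol with placebo is not affected.

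**What to change.** In section 7c, replace the simple regressions with one model per marker and outcome, using both arms:

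week-12 score = outcome's baseline score + arm + marker + arm × marker (+ EIBI intensity)

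- When the PAS is both marker and outcome, enter baseline PAS once and test arm × baseline PAS. Entered twice, the design matrix has 5 columns but rank 4; entered once, it has 4 columns and rank 4.
- For the CGIC, a "7-point subjective scale assessing change from baseline", there is no baseline score, so omit that term.
- Report the arm × marker coefficient with its 95% confidence interval, label it exploratory, and state how many marker–outcome pairs were tested (at least 27).
- Do not describe a marker as predicting response to propranolol on the strength of a pooled or single-arm slope.

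Week 12 is used as the end-of-treatment visit. A model that also used week 6 would serve, provided it carries the arm × marker term.

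The cost is wording only, since markers and outcomes are already collected in both arms. The drawback is imprecision: 80% power needs a slope difference of about 1.2 residual SD per SD of marker, so a null result would be uninformative. The gain is a correctly interpreted estimate, not a powered test.
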